The patients in the control group will undergo iliac crest bone graft surgery per the surgeon’s usual practice. The treatment group will be managed in a similar fashion, with the rhBMP-2/ACS placed at the site of bone defect on a collagen sponge carrier per manufacturer’s instructions. The patients will receive crushed cancellous allograft packed into the defect prior to an overlay of the rhBMP-2/ACS. The maximum amount of allograft chips is 60 cc to be used to fill the defect. The allograft chips will be loosely packed to fill the cortical defect flush to the cortical bone. After the allograft is implanted into the site and there is an adequate hemostasis, the RhBMP2 sponge will be applied as an overlay covering the allograft and bridging the proximal and distal tibial fragment of the defect; that is laying flat on the surface. The sponge is not to be folded, rolled or placed in any other configuration. The sponge requires no sutures to be held in place. If the patient requires more than one large pack of Infuse, they will be excluded from the study. This RhBMP2/ACS implant will be placed directly adjacent to viable muscle bed. A drain will not be used. Wound closure will commence when hemostasis is obtained. The amount of cancellous chips and brand used will be recorded on the case report form.

Medtronic Sofamer Danek markets rhBMP-2/ACS as INFUSE Bone Graft. They have agreed to provide kits of rhBMP-2 to the 25 patients randomized to the treatment group. This donation is unrestricted. Medtronic Sofamer Danek will not be a participant in the study, nor will have any access to patient or study data or any input into data analysis, results and presentations.

The patients in both groups will be evaluated at 2 weeks, 6 weeks, 12 weeks, 18 weeks, 6 months and 12 months. Outcome measures will be “union,” “wound healing and infection,” and “need for further intervention.” Pain will be documented using the Visual Analogue Scale (VAS) at each visit. Short Form-12 (SF-12) and the Short Musculoskeletal Functional Assessment (SMFA) will be completed at 6 months and 12 months. Billing information will be obtained at the end of the 12 month study period to estimate cost of care in both treatment groups.

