### **Consent Procedures**

## **IRB00003098 Funding Protocol rhBMP-2/ACS vs. Autograft for Critical Size Tibial Defects**

Written consent will be obtained during the clinic visit when bone graft surgery is scheduled. Prior to bone grafting procedure, female patients will be given a pregnancy test. Those with a positive pregnancy test will no longer be eligible and will receive standard treatment (iliac crest autograft). Patients with an active infection at the operative site, purulent drainage from the fracture or evidence of active osteomyelitis are not eligible for the study. Active infection will be defined clinically by skin changes, including redness, warmth and active drainage. Additionally, the diagnosis can be supported by laboratory values, including elevated WBC, ESR and CRP. Osteomyelitis is suspected by radiographic evidence of lytic lesions. If, at the time of surgery, the surgeon is concerned that the patient has a deep wound infection because of intra-operative findings that may include loose hardware, purulence or an inflammatory tissue reaction – the patient will be excluded from the study.

Informed consent will be obtained before any study procedures are initiated. The consent form will be reviewed in its entirety with the patient by the surgeon and research coordinator and all questions will be answered. Investigators will ask the subject questions to assure understanding before the consent for participation in the study is signed, specifically:

1. Can you explain what it means to be involved in this study?
2. What should you do if you no longer want to participate in the study?

If the patient cannot answer these questions, the patient will be deemed by the investigator to be incapable of providing informed consent secondary to a lack of mental competence; the subject will not be enrolled into the study.

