### Duration/Follow-up Schedule

It is anticipated that the required patients will be enrolled into this study during an 18-month period and will be followed for one year. Thus, the data collection time is anticipated to be a 2.5 year period. The patients will be evaluated at 2 weeks, 6 weeks, 12 weeks, 18 weeks, 6 months and 12 months according to the following schedule:

Follow-Up Schedule	Process	Data Collected
Enrollment	Clinical examination	Inclusion/Exclusion criteria, patient characteristics, fracture characteristics, surgical summary, VAS
2 weeks	Clinical examination, functional outcomes	Clinical follow-up data, VAS
6 weeks	Clinical examination, functional outcomes, radiographs	Clinical follow-up data, VAS
12 weeks	Clinical examination, functional outcomes, radiographs	Clinical follow-up data, VAS
18 weeks	Clinical examination, functional outcomes, radiographs	Clinical follow-up data, VAS
6 months	Clinical examination, functional outcomes, radiographs	Clinical follow-up data, VAS, SF12, SMFA
12 months	Clinical examination, functional outcomes, radiographs	Clinical follow-up data, VAS, SF12, SMFA

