## **Measurements**

Effectiveness Evaluation (x-ray, weight bearing, 2nd procedures)

Outcome measures will be “radiographic union,” “clinical union”, “wound healing and infection,” and “need for further intervention.”

Pain-will be documented using the Visual Analogue Scale (VAS) at each visit.

Short Form-12 (SF-12), Short Musculoskeletal Functional Assessment (SMFA) will be completed at 6 months and 12 months.

The **SF-12** questionnaire was developed from the Medical Outcomes Study. It is a self-administered, 12-item questionnaire that measures health-related quality of life in 8 domains. Both physical and mental summary scores can be obtained. Each domain is scored separately from 0 (lowest level) to 100 (highest level). The instrument has been extensively validated and has demonstrated good construct validity, high internal consistency, and high test-retest reliability. Our decision to use the SF-12 over other available instruments was based on its widespread use in orthopaedics, its use in previous studies evaluating fracture outcomes, and the strong evidence of validity.

The **SMFA** is a shorter version of the 101 item Musculoskeletal Function Assessment (MFA) questionnaire. The SMFA is a 46 item questionnaire consisting of the dysfunction and bother index. The dysfunction index has 34 items for assessment of patient function, while the bother index consists of 12 items designed to detect how much patients are bothered by functional items. The SMFA has been evaluated for reliability, validity and responsiveness in patient populations. We chose this scale because it is a short, validated instrument to provide us with information regarding the patient’s functional status.

Safety Evaluation (complications, re-operations, adverse events)

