### **Statistical Analyses/Data Presentation**

### Sample Size Justification

To address our primary objective, a comparison of healing rates between BMP and Autogenous Bone Grafts, we assume at 20% higher healing rate in BMP treated patients ( Jones et al, 2006), with a baseline healing rate of 65% (with autogenous bone graft). Stipulating a study power of 80% and an alpha level=0.05, and a non-inferiority margin of 20% our study will require at least 14 patients per treatment arm. If we stipulate our non-inferiority margin to be 10%, we will require 25 patients per group. Thus, to be most conservative, our study will recruit 50 patients total (25 patients per treatment arm). We will complete an interim evaluation of results once 25 patients have been enrolled, including a power analysis.

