### Final Analysis

The results will be reported comparing the outcomes in the groups at each follow-up period. It is anticipated that the required patients will be entered into the investigation during an 18-month period and will be followed for one year. Thus, the data collection time will be a 2.5- year period. We believe that at that time, the results of the study will reveal whether any differences exist with this high-energy disabling fracture in terms of outcomes, union rates, times to union, soft-tissue complications and infection rates.

Data will be analyzed on an intent to treat basis (patient data included in the treatment group and stratum to which randomized). Fishers exact test will be used to compare categorical variable and the Student t test will be used for continuous variables for comparisons between the two groups.

Quality of life data will be coded and scored according to the guidelines provided with the SMFA (Coding Key Manual, Musculoskeletal Function Assessment, Injury and Arthritis Survey) and the SF-12 (Coding Manual for the SF-12 Health Survey).

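### VAS pain is recorded at enrolment, but the only stated test for continuous variables is an unadjusted t test; baseline adjustment would probably gain precision at little cost

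*Combined protocol and SAP*

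**What the plan says.** The Duration/Follow-up Schedule table lists these data for the enrolment row: "Inclusion/Exclusion criteria, patient characteristics, fracture characteristics, surgical summary, VAS". It lists VAS again at 2, 6, 12 and 18 weeks and at 6 and 12 months. The Protocol section agrees ("Pain will be documented using the Visual Analogue Scale (VAS) at each visit"), and so does Measurements.

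Under Consent Procedures, "Written consent will be obtained during the clinic visit when bone graft surgery is scheduled", so a value taken at enrolment can precede the graft.

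Final Analysis gives the whole method for continuous outcomes. On timing: "The results will be reported comparing the outcomes in the groups at each follow-up period". On the test: "the Student t test will be used for continuous variables for comparisons between the two groups". It does not mention VAS by name, and no section describes a covariate, a change score or a repeated-measures model.

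SF-12 and SMFA are different: "Short Form-12 (SF-12), Short Musculoskeletal Functional Assessment (SMFA) will be completed at 6 months and 12 months". They have no enrolment value, so this point concerns VAS only.

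**The concern.** Pain is part of the case for the trial. The Purpose section gives harvest-site pain as a limitation of iliac crest graft, the risk section for standard treatment lists it, and Steps to Minimize Risk names reduced pain as a possible benefit of rhBMP-2. VAS is also the only patient-reported scale with an enrolment value.

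With 25 per arm, precision is scarce. A comparison of follow-up values that leaves out the enrolment value gives up whatever that value predicts. Nothing in the design balances starting pain either, because randomisation is blocked within centre with no subgroups. What is at stake is a wider interval for the pain difference than the collected data would allow.

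**Working it through.** **The plan's own figures.** The documents state no SD, effect size or power for VAS. The only sample-size figures are for union: 14 per arm at a 20% margin and 25 per arm at a 10% margin. With healing of 65% and 85%, one-sided alpha 0.05 and 80% power:

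n = (1.645 + 0.842)² × (0.65×0.35 + 0.85×0.15) / (0.20 + margin)² = 6.18 × 0.355 / (0.20 + margin)²

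This gives 13.7, rounded up to 14, at a 20% margin, and 24.4, rounded up to 25, at a 10% margin. Both stated figures reproduce. They concern union only, and nothing below alters them.

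**Inputs for VAS.** There are 25 patients per arm, so N = 50 (Sample Size Justification). The correlation rho between enrolment and follow-up VAS is not given, so it is an assumption shown over a range. Complete VAS data, a linear relation and equal variances are also assumed.

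**Unadjusted t test.** The SE of the difference is SD × √(2/25) = 0.283 SD. At two-sided 0.05 and 80% power (assumed for VAS), the detectable difference is (1.960 + 0.842) × 0.283 = 0.79 SD by normal approximation, or 0.81 SD with the exact t.

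**Chance imbalance.** The enrolment difference between arms has the same SE, 0.283 SD. An imbalance of 0.3 SD or more in either direction has z = 0.3/0.283 = 1.06, a probability of about 29%.

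**Adjusted analysis.** Adjustment multiplies the variance of the difference by (1 − rho²). Estimating the slope costs a factor of 1 + 1/(N − 4) = 1 + 1/46 = 1.0217. The net factor is F = (1 − rho²) × 1.0217. Equivalent patients per arm are 25/F, relative interval width is √F, and the detectable difference is 0.792 × √F.

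| Assumed rho | F | Equivalent per arm | Relative interval width | Detectable difference (SD) |
|---|---|---|---|---|
| 0 | 1.02 | 24.5 | 1.01 | 0.80 |
| 0.1 | 1.01 | 24.7 | 1.01 | 0.80 |
| 0.3 | 0.93 | 26.9 | 0.96 | 0.76 |
| 0.5 | 0.77 | 32.6 | 0.88 | 0.69 |
| 0.7 | 0.52 | 48.0 | 0.72 | 0.57 |

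A simulation of 20,000 trials per setting gave variance ratios of 1.024, 1.016, 0.925, 0.760 and 0.520 for the same five correlations, in agreement with F.

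**Break-even.** F = 1 when rho² = 1 − 46/47, so rho is about 0.15. The worst case, at rho = 0, is 1/46, or about 2% more variance.

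**If change scores were meant.** Their variance factor is 2(1 − rho): 1.4, 1.0 and 0.6 at rho 0.3, 0.5 and 0.7. That beats raw values only above rho 0.5, and it is larger than F at each of these values.

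**The case against.** Five arguments can be made for leaving the plan alone.

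- **Status of VAS.** No research question or null hypothesis concerns pain, and the outcome measures listed are union, wound healing and infection, and further intervention. Pain is documented alongside them. This stands, and it limits the importance of the point.
- **Validity.** A reader might infer that the t test is biased, or that its result cannot be trusted if starting pain differs by chance. The documents do not support this. Under randomisation the test is valid, and its standard error already allows for chance imbalance. Adjustment makes the estimate more precise; it does not repair an invalid one.
- **Unknown gain.** A reader might infer that adjustment always narrows the interval and costs nothing. It does not: below a correlation of about 0.15 there is no gain. The correlation could be low. Donor-site pain does not exist before harvest and arises only in the control arm, the body site for VAS is not specified, and 12 months is a long interval. This stands as a limit on the expected benefit. It does not reverse the choice, because the possible loss is about 2% of variance and the possible gain is much larger.
- **Silence on raw or change scores.** Final Analysis does not say which is tested. Raw values at each visit is the plain reading, but it is an inference from a general sentence. Change scores would not remove the point, as the working shows.
- **Timing of the enrolment value.** The enrolment row also lists the surgical summary, so the table alone does not establish that VAS is taken before the graft. Adjusting for a later value would mean adjusting for something the treatment may have affected. This stands, and the fix has to deal with it.

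**Conclusion.** The point holds as one of lost precision on a measure that is documented but not tied to a hypothesis. An enrolment VAS is scheduled, the only stated method for continuous variables is an unadjusted t test, and no section provides for adjustment. With 50 patients, adjustment would cut the variance of the VAS difference by about 7%, 23% or 48% at assumed correlations of 0.3, 0.5 or 0.7. It would give nothing below about 0.15, and at worst would add about 2%. These figures rest on an assumed correlation, complete VAS data and an enrolment value taken before the graft.

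A reader might also infer that the trial is underpowered for union because of this, or that SF-12 and SMFA share the problem. Neither follows: union is a separate analysis, and those two scales have no enrolment value to adjust for. The change is worth making because it is cheap and the outcome bears on the trial's rationale.

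**What to change.** In Final Analysis, exempt VAS from the t test and specify one model, for example: *VAS at each follow-up visit will be compared between arms by a linear model with treatment arm and enrolment VAS as terms; 12 months is the main time point; the adjusted mean difference and its 95% confidence interval will be reported. The enrolment VAS used is the value recorded before the graft procedure.* Make the same timing explicit in the enrolment row of the schedule.

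The t test can remain for SF-12 and SMFA. Settle the model before outcome data are seen, so that adjustment is not chosen according to the result.

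The cost is a few sentences of text, one degree of freedom in each visit's model, and a negligible loss of precision if the correlation is very low. No new data are needed, provided the enrolment VAS is in fact taken before the graft.

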### **Data Security and Protection Plan**

All data will be collected on Case Report Forms provided to the participating sites by the Coordinating Center. The research coordinators at each site will obtain the information necessary to complete the case report forms (CRFs) from several sources including the patient's medical record, clinical evaluations and patient interviews. These forms will NOT contain the patient's name, SSN, or hospital medical record number; they will be identified only by a unique patient-specific study number.

The Site Research Coordinator will enter non-personally identifiable information into a central and secured web-based data management system being implemented for all Consortium studies, known as REDCap. This data management system has incorporated state-of-the-art features for electronic data collection and is configured in accordance with best practices for information technology and research data management

## **IRB00003098 Funding Protocol rhBMP-2/ACS vs. Autograft for Critical Size Tibial Defects**

Hard copy documents containing subject data and patient identifiers (and contact information) will be stored in secure document containers (file cabinets, lockers, drawers, etc.) in accordance with standard document management practices. The data collection forms will be destroyed within five years after study completion, as will the file linking study numbers with personally identifiable information. Paper forms will be shredded and the file containing personally identifiable data at each site will be deleted from local site computers. Each site will provide the Coordinating Center a signed verification that these data have been destroyed.

All research data, in hard copy or electronic form, will be stored and managed in a secure manner following applicable federal regulations and guidelines and according to institutional policies and practices.

At all times, only listed key personnel specifically designated and authorized by the Principal Investigator shall have access to any research related documents, including electronic data. All such personnel will be properly trained and supervised regarding the management and handling of confidential materials. The Principal Investigator assumes full responsibility for such training, supervision, and conduct

### **Risk Analysis**

Risks Associated with Experimental Treatment: The use of rhBMP-2 in the staged bone grafting of a tibial shaft fractures with a bone defect is currently off-label. BMP-2 is approved for extremity trauma for open tibial shaft fractures within the first 14 days after injury. However, we are not intending to support a new indication for its use or not intending to support a significant change in advertising for the product; the route and dosing of administration and subject population is the same as currently used according to FDA approvals; the study will be conducted in compliance with IRB review and informed consent and also in compliance with the requirements concerning the promotion and sale of the drug and it does not intend to invoke the Humanitarian Device Exemption. Based on the result of animal and human studies, rhBMP-2 may help bone to heal faster than it normally would without rhBMP-2. It is possible that the subject will get the BMP-2 treatment but do less well than he/she would have done with standard care alone. Also because the treatment is relatively new, we may not yet know the side effects: something unexpected could happen.

Possible risks of rhBMP-2 (the side effects reported by 1% to 10% of all patients studied) were:

- Headache
- Increased amount of amylase (an enzyme used in digestion), in the blood without obvious signs of pancreatitis (inflammation of the pancreas)
- Tachycardia (fast heart beat)
- Decreased magnesium in the blood

It is possible for women of child bearing age to develop antibodies to BMP. In clinical experience, antibodies develop in approximately 1-5% of patients who receive the treatment. The effect of a mother's antibodies on an unborn baby is not known, both when the antibodies are detected and later. Women who are able to have children will need to take measures to prevent pregnancy for one year after treatment with BMP. Examples of birth control methods include, but are not limited to, birth control pills, intrauterine device (IUD), birth control implant, birth control patch and diaphragm. Your doctor can further discuss birth control options with you.

PREGNANCY: The following boxed warning is present on the current labeling for INFUSE® Bone Graft:

- In an experimental rabbit study, rhBMP-2 has been shown to elicit antibodies that are capable of crossing the placenta. Reduced ossification of the frontal and parietal bones of the skull was noted infrequently (<3%) in fetuses of rabbit dams immunized to rhBMP-2; however, there was no effect noted in limb bud development. There are no adequate and well-controlled studies in human pregnant women. Women of child bearing potential should be warned by their surgeon of potential risk to a fetus and informed of other possible orthopedic treatments.
- Women of childbearing potential should be advised that antibody formation to rhBMP-2 or its influence on human fetal development has not been assessed. In the clinical trial supporting the safety and effectiveness of the INFUSE Bone Graft in tibia fractures, 9/149 (6.0%) patients treated with INFUSE Bone Graft and 1/150 (0.7%) patients treated without exposure to rhBMP-2 developed antibodies to rhBMP-2. The effect of maternal antibodies to rhBMP-2, as might be present for several months following device implantation, on the unborn fetus is unknown. Additionally, it is unknown whether fetal expression of BMP-2 could re-expose mothers who were previously antibody positive. Theoretically, re-exposure may elicit a more powerful immune response to BMP-2 with possible adverse consequences for the fetus. However, pregnancy did not lead to an increase in antibodies in the rabbit study. Studies in genetically altered mice indicate that BMP-2 is critical to fetal development and that a lack of BMP-2 activity may cause neonatal death or birth defects. It is not known if anti-BMP-2 antibodies may affect fetal development or the extent to which these antibodies may reduce BMP-2 activity.
- INFUSE® Bone Graft should not be used immediately prior to or during pregnancy. Women of childbearing potential should be advised not to become pregnant for one year following treatment with the INFUSE® Bone Graft.
- The safety and effectiveness of the INFUSE® Bone Graft in nursing mothers has not been established. It is not known if BMP-2 is excreted in human milk.

Safety data has not been established in females who are pregnant or nursing, and these patients will be excluded from this study. Females will undergo serum pregnancy testing in order to rule out pregnancy prior to implantation of INFUSE® Bone Graft. Informed Consent will inform subject's that INFUSE® Bone Graft has not been tested in pregnant or nursing women. Female

subjects with child-bearing potential will be advised to use oral contraceptives and/or refrain from becoming pregnant for 12 months following implantation. These precautions should minimize any potential risk to female patients and/or their fetus. If a subject becomes pregnant after implantation of INFUSE® Bone Graft the Investigator will document pregnancy as an AE, advise the subject to notify their obstetrical physician, monitor for occurrence of additional AEs, and report findings related to pregnant and/or nursing females in the annual and final report.

